## **6.7 BASELINE, TIME WINDOWS AND CALCULATED VISITS**

Unless otherwise specified baseline is defined as the time point closest to but prior to the first administration of any study medication. If no time is specified and the date is the same as the first administration date, then it will still be considered baseline if not specified otherwise. If there is no measurement earlier than the first administration of study medication, then no baseline will be derived.

Study day will be calculated relative to the date of the first administration of study drug. The day prior to first administration of study drug will be 'Day -1' and the day of first administration of study drug will be 'Day 1'; therefore 'Day 0' will not exist.

#### Imaging time windows:

Time windows and visits will be calculated to determine the planned day of tumour measurement and response status, based on the protocol-specified tumour imaging schedule.

For the presentation of tumour response data which will follow a calculated visit approach

based on the protocol specified tumour imaging schedule. Imaging will be performed at screening and every 6 weeks after BI 754091 infusion (i.e. Week 6, 12, 18 ...etc.), then every 9 weeks after 6 months of treatment; image data will be slotted to Week 6, 12, 18 etc. based on their relative day (from start of treatment) and using a  $\pm 3$  week window (images taken in the first 3 weeks from start of treatment will be assigned to Week 6). If two or more images for a patient are assigned to one interval then the last assessment will be used to ensure progressive disease is not missed.

In order to identify whether consecutive imaging time points are missing for a given patient, a nominal time point (i.e. Week 6, 12, 18 ... etc.) will be assigned to each and every image. This is achieved by creating windows for every radiological response assessment. These windows are defined in [Table 6.7: 1](#).

Table 6.7: 1 Nominal time points and windows for imaging

Nominal time point (weeks from start of study medication)	Due date of scans (days)*	Window (days)
6	43	1 to $\leq$ 64
12	85	65 to $\leq$ 106
18	127	107 to $\leq$ 148
24	169	149 to $\leq$ 200
33	232	201 to $\leq$ 263
42	295	264 to $\leq$ 326
51	358	327 to $\leq$ 389
Etc., 9 week interval	Etc.	Etc.

\* The date of the first dose of study medication is Day 1

If a patient does not have an image in one of the windows described above, he/she will be considered to have missed an assessment for that time point.

#### Laboratory values:

Baseline is defined as the latest time point before the very first administration of any study medication. For laboratories where not only the examination date but also time are recorded, examination time has to be taken into account when defining baseline. That is, a laboratory value on the same date as the first administration of study medication is considered as baseline value if and only if the time of laboratory assessment is before or the same as the time of first study drug administration.

If any of these times is missing and the date of laboratory assessment is equal to the date of first administration of study medication, then the laboratory assessment will be considered as according to protocol, i.e. as prior to first study medication.

#### Laboratory time windows:

Time windows and visits will be calculated to determine the planned day of laboratory assessment, based on the protocol-specified laboratory assessment schedule.

For the presentation of a descriptive summary analysis over time for a laboratory parameter the laboratory data will be displayed by calculated visit instead of actual visit reported to ensure a common handling of all laboratory assessments and to account for unscheduled visits representing a repeated laboratory measurement. As Phase Ia and Phase Ib have a different laboratory assessment schedule, the time windows for the calculated visits will be different for Phase Ia and Phase Ib.

Table 6.7: 2 Calculated visits, nominal time points and windows for laboratory assessments in Phase Ia

Calculated visit	Nominal time point (weeks from start of study medication)*	Window (days)
Cycle 1 Day 1	1	1 to $\leq$ 4
Cycle 1 Day 8	8	5 to $\leq$ 11
Cycle 1 Day 15	15	12 to $\leq$ 18
Cycel 2 Day 1	22	19 to $\leq$ 32
Cycle 3 Day 1	43	33 to $\leq$ 53
Cycle 4 Day 1	64	54 to $\leq$ 74
Etc., 21 days interval	Etc.	Etc.

\* The date of the first dose of study medication is Day 1

Table 6.7: 3 Calculated visits, nominal time points and windows for laboratory assessments in Phase Ia

Calculated visit	Nominal time point (weeks from start of study medication)*	Window (days)
Cycle 1 Day 1	1	1 to $\leq$ 11
Cycel 2 Day 1	22	12 to $\leq$ 32
Cycle 3 Day 1	43	33 to $\leq$ 53
Cycle 4 Day 1	64	54 to $\leq$ 74
Cycel 5 Day 1	85	75 to $\leq$ 95
Cycle 6 Day 1	106	96 to $\leq$ 116
Cycle 7 Day 1	127	117 to $\leq$ 137
Cycel 8 Day 1	148	138 to $\leq$ 158

Table 6.7: 3 Calculated visits, nominal time points and windows for laboratory assessments in Phase Ia (cont.)

Calculated visit	Nominal time point (weeks from start of study medication)*	Window (days)
Cycle 9 Day 1	169	159 to $\leq$ 179
Cycle 12 Day 1	232	180 to $\leq$ 1263
Cycel 15 Day 1	295	264 to $\leq$ 326
Cycle 18 Day 1	358	327 to $\leq$ 389
Etc., 21 days interval	Etc.	Etc.

\* The date of the first dose of study medication is Day 1

Biomarker time windows:

The time windows used for biomarker analysis are defined as follows.

## **7. PLANNED ANALYSIS**

For End-Of-Text (EoT) tables, the set of summary statistics is: N / Mean / Standard deviation (StD) / Min / Median / Max.

For tables that are provided for endpoints with some extreme data, median, quartiles and percentiles should be preferred to Mean, StD, Min and Max.

For time-to-event analysis tables the set of statistics is: number of patients [N(%)], number of patients with event [N(%)], <time to event> [months] followed by P25 (25th percentile), median, P75 (75th percentile) and number of patients censored [N(%)]. If not specified otherwise the duration as well as the time to event will be displayed in months.

Tabulations of frequencies for categorical data will include all possible categories and will display the number of observations in a category as well as the percentage (%) relative to the respective treatment group (unless otherwise specified, all patients in the respective patient set whether they have non-missing values or not). Percentages will be rounded to one decimal place. The category missing will be displayed only if there are actually missing values.

Sort order for general categorical variables: If categories correspond to the collected categories on the eCRF and the table shells do not explicitly specify the ordering, the “default ordering” defined by the eCRF is to be used in such cases. If categories are derived, the ordering as specified in the table shell document should be used; in general ordinal data (e.g. categorised continuous data) are to be displayed in ascending order. Abbreviations (e.g. Wors.) should not be displayed without any explanations. They will be either spelled out in the table or explained in footnotes (whatever is more reasonable from the programming point of view).

If applicable, conversion from days to weeks, months and years will be as follows:

- Weeks = Days / 7
- Months = (Days \* 12) / 365.25
- Years = Days / 365.25

[REDACTED] history, prior anti-cancer therapies, medical history and baseline disease assessment.

## **7.2 CONCOMITANT DISEASES AND MEDICATION**

Only descriptive statistics are planned for this section of the report. Concomitant diseases will be coded similarly as adverse events based on the most current Medical Dictionary for Regulatory Activities (MedDRA) version. Concomitant therapies (CTs) will be coded according to World Health Organization Drug Dictionary (WHO DD). CTs will be classified according to the Anatomical Therapeutic Chemical (ATC) classification system. The third ATC level will be used to categorise CTs by therapy type. In situations where a medical product may be used for more than one equally important indication, there are often several classification alternatives. As appropriate, patients receiving CTs with more than one possible ATC level 3 category will be counted more than once. Footnotes will clarify this possible double counting in tables.

## **7.3 TREATMENT COMPLIANCE**

Not applicable in this study.

## **7.4 PRIMARY ENDPOINT(S)**

### **7.4.1 Primary analysis of the primary endpoint(s)**

In order to identify the MTD and the recommended dose for the Phase Ib dose expansion phase, the number of patients with DLTs at each dose level during the Phase Ia MTD evaluation period (first three weeks) must be presented. Patients who discontinue during the first treatment course for reasons other than a DLT will be excluded from the determination of the MTD.

The analysis of the MTD is based on a BLRM guided by the escalation with overdose control principle. The MTD is defined as the highest dose for a given schedule that is expected to cause less than 25% risk of the true DLT rate being above or equal to 33% during the MTD evaluation period. Estimation of the MTD during the dose escalation phase of the study will be based upon the estimation of the posterior probability of the incidence of DLT in toxicity categories during the MTD evaluation period for all evaluable patients. The model to be used is specified in CTP Section 7.

Tables and bar charts displaying the posterior probabilities of the true DLT rates being in either the underdosing interval, the targeted toxicity interval or the over toxicity interval will be produced.

For Phase Ib dose expansion, OR according to RECIST v1.1 will be analysed in terms of

objective response rate (ORR), defined as the proportion of patients with best overall response of CR or PR. ORR according to RECIST v1.1 will be summarised descriptively with 95% exact Clopper-Pearson confidence intervals (CIs).

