7.3.1 Primary endpoint analyses

In order to identify the MTD of the trial, the number of patients with DLTs at each dose level during the Phase Ia MTD evaluation period (first three weeks) must be presented. Patients who discontinue during the first treatment course for reasons other than a DLT will be excluded from the determination of the MTD.

In addition, the number of patients with DLTs that occurred during the entire treatment period, including Phase Ia and Phase Ib, will be summarised at each dose level. The BLRM will be rerun to re-evaluate the MTD and RP2D together with all relevant data collected during Phase Ib.

For the primary efficacy endpoint of Phase Ib, objective response rate (ORR) will be summarised and presented with 95% two-sided confidence intervals using the Clopper-Pearson method.

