7.4 INTERIM ANALYSES

The sponsor will continuously monitor the safety. The dose-escalation design dictates that the sponsor and the SRC perform regular safety evaluations. These evaluations will be unblinded to dose.

If considered necessary, as soon as the MTD is determined, an evaluation of the safety aspects will be performed. Results of this evaluation will be documented and archived. If applicable, such an analysis will be defined in more detail in the TSAP.

No formal interim analysis of PK data is planned. However, an exploratory analysis of PK will be done after patients in Cohort 1 complete Cycle 1 and once patients in Cohort 2 complete Cycle 1. Further exploratory analyses of PK might be performed if considered reasonable.

Exploratory PK analyses will be based on planned sampling times, if information on actual times should not be available. The results of these evaluations will be preliminary and may be subject to change, as these do not involve a formal database lock. No interim report will be written for exploratory PK analyses. If medically justified, further or fewer exploratory PK analyses may be performed.

Interim efficacy analyses are planned for selected groups of patients (defined in Section 3.1) in the Phase Ib portion of the trial. Because of the expected challenge in recruiting these patients, the two-stage design is planned to stop further recruitment of the specific patient group if the defined efficacy boundary (see Table 7.4: 1) is not met at the first stage. Interim efficacy analyses were not deemed necessary for the TMB high cohort 5 as recent literature already demonstrates an association between high TMB and better response rates for patients taking immune checkpoint inhibitors (R18-1492).

The interim analyses for Cohort 6 will be conducted when:

- 10 patients with squamous cervical and/or anal cancer have been treated, and the 10th patient has been on treatment for ~3 months.
- 10 patients with squamous skin tumours have been treated, and the 10th patient has been on treatment for ~3 months.

The interim analysis for Cohort 7 will be conducted when 20 patients with vaginal or VSCC have been treated, and the 20th patient has been on treatment for ~3 months.

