It has been calculated that with an earlier interim point, the probabilities of false early stopping or observing a false positive/negative result at the final analysis will be too high. With a later interim point, the false positive, false negative and false early stopping probabilities will be improved, but the scale of improvement is not that meaningful.

- Literature on preliminary data of nivolumab and pembrolizumab ([R17-3902](#); [R17-3903](#); [R17-3822](#)) showed ORR ranges from 13% to 24% in patients with squamous cervical and anal tumours. Therefore, an underlying ORR of 25% is assumed. The probability of observing zero responders out of 10 and stopping at interim is 6%, and the probability of observing $\geq 20\%$ ORR at final analysis is 77%. If the underlying ORR is 5%, the probability of stopping early is 61%, and the false positive probability of observing $\geq 20\%$ ORR at final analysis is almost 0.
- It was shown in Chalmers ZR et al, 2017 ([R17-3824](#)) that the population with squamous skin cancer had very high proportion of patients with high TMB (~70%). Therefore, the clinical benefit is expected to be similar to patients with high TMB ([R17-3768](#)). Assume the underlying ORR is 50%, the probability of observing < 3 responders out of 10 and stopping at interim is 5%, and the probability of observing $\geq 40\%$ ORR at final analysis is 87%. If the underlying ORR is 20%, the probability of stopping early is 67%, and the false positive probability of observing $\geq 40\%$ ORR at final analysis is 1%.
- Literature on preliminary data from older chemotherapy/targeted agent trials ([R18-2645](#); [R18-2646](#); [R18-2647](#)) and early phase immunotherapy trials ([R18-2650](#); [R18-2651](#)) showed ORR ranges from 13% to 29% in patients with recurrent, inoperable VSCC. Therefore, an underlying ORR of 25% is assumed. The probability of observing 0 or 1 responder out of 20 and stopping at interim is 2%, and the probability of observing $\geq 20\%$ ORR at final analysis is 82%. If the underlying ORR is 5%, the probability of stopping early is 74%, and the false positive probability of observing $\geq 20\%$ ORR at final analysis is almost 0.

Table 7.4: 1 Early stopping criterion and probabilities for the two-stage approach – selected patient groups

Assumed underlying ORR	Total sample size	Stage 1 sample size	Early stopping criterion (observed ORR)	Early stopping prob.	Observed ORR at final	Probability of observed ORR at final

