Squamous cervical or anal tumour patients						
5%	30	10	<10% (< 1 out of 10)	61%	>=20% (>= 6 out of 30)	0%
10%	30	10	<10% (< 1 out of 10)	35%	>=20% (>= 6 out of 30)	7%
15%	30	10	<10% (< 1 out of 10)	19%	>=20% (>= 6 out of 30)	29%
20%	30	10	<10% (< 1 out of 10)	11%	>=20% (>= 6 out of 30)	55%
25%	30	10	<10% (< 1 out of 10)	6%	>=20% (>= 6 out of 30)	77%
30%	30	10	<10% (< 1 out of 10)	3%	>=20% (>= 6 out of 30)	91%
Squamous skin cancer patients						
20%	30	10	<30% (< 3 out of 10)	67%	>=40% (>= 12 out of 30)	1%
25%	30	10	<30% (< 3 out of 10)	52%	>=40% (>= 12 out of 30)	5%
30%	30	10	<30% (< 3 out of 10)	39%	>=40% (>= 12 out of 30)	14%
35%	30	10	<30% (< 3 out of 10)	26%	>=40% (>= 12 out of 30)	33%
40%	30	10	<30% (< 3 out of 10)	17%	>=40% (>= 12 out of 30)	54%
45%	30	10	<30% (< 3 out of 10)	10%	>=40% (>= 12 out of 30)	73%
50%	30	10	<30% (< 3 out of 10)	5%	>=40% (>= 12 out of 30)	87%
Vaginal or VSCC patients						
5%	40	20	<10% (< 2 out of 20)	74%	>=20% (>= 8 out of 40)	0%
10%	40	20	<10% (< 2 out of 20)	39%	>=20% (>= 8 out of 40)	4%
15%	40	20	<10% (< 2 out of 20)	18%	>=20% (>= 8 out of 40)	25%

Assumed underlying ORR	Total sample size	Stage 1 sample size	Early stopping criterion (observed ORR)	Early stopping prob.	Observed ORR at final	Probability of observed ORR at final
20%	40	20	<10% (< 2 out of 20)	7%	>=20% (>= 8 out of 40)	56%
25%	40	20	<10% (< 2 out of 20)	2%	>=20% (>= 8 out of 40)	82%
30%	40	20	<10% (< 2 out of 20)	1%	>=20% (>= 8 out of 40)	94%

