7.7.2 Determination of sample size for Phase Ib

For the cohort of 7 solid tumours (Cohort 4), no formal statistical sample size calculations were performed. Some efficacy signals are expected to be observed from ~30 treated patients.

Several papers demonstrated the association between high TMB and better response rates, progression-free survival, and overall clinical benefit. In Hellmann et al., 2018 ([R18-1492](#)) response rates were 45.3% (63/139) in patients with ≥ 10 mutations/mega base. Therefore, in the planning of the TMB-high-tumour cohort (Cohort 5), it is deemed clinically meaningful if BI 754091 will have an underlying ORR of 35%. With 30 patients, an ORR of 30% or more would be observed with a probability of 78% assuming a true response rate of 35%. The probability of observing a false positive signal, e.g., to observe at least an ORR of 30% if the underlying true ORR is 15%, is around 3%. [Table 7.7.2: 1](#) summarises the probability of observing certain ORRs based on different assumptions of the underlying ORR.

Table 7.7.2: 1 Probabilities of observing certain objective response rates

Assumed underlying ORR	Sample size	Probability to observe at least		
		ORR >= 25% (>=8 responders)	ORR >= 30% (>=9 responders)	ORR >= 35% (>= 11 responders)
15%	30	7%	3%	0%
20%	30	24%	13%	3%
25%	30	49%	33%	11%
30%	30	72%	57%	27%
35%	30	88%	78%	49%
40%	30	96%	91%	71%
45%	30	99%	97%	86%

For the selected squamous tumours cohort (Cohort 6), probability calculations are provided in [Table 7.4: 1](#) using the two-stage approach. Depending on the Stage 1 result for the squamous cohort, sample size may vary between 20 and 60 patients.

For the vaginal or VSCC cohort (Cohort 7), probability calculations are provided in Table 7.4: 1 using the two-stage approach. If the stage 1 result is positive (i.e., at least 2 responders out of 20 patients), sample size for this cohort will be increased to 40 patients; otherwise, recruitment will be stopped in case of negative interim analysis.

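### The Clopper-Pearson interval planned for ORR is not exact in the three groups with a futility stop, and its upper limit is too low for groups that continue and end with few responders

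*SAP*

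**What the plan says.** Protocol 7.4 sets up the futility look: "the two-stage design is planned to stop further recruitment of the specific patient group if the defined efficacy boundary" is not met. Table 7.4: 1 gives the rules. Cervical/anal stops at 0/10, otherwise 30 patients; skin stops below 3/10, otherwise 30; vaginal/VSCC stops below 2/20, otherwise 40. For VSCC, protocol 7.7.2 repeats that after a positive first stage "sample size for this cohort will be increased to 40 patients; otherwise, recruitment will be stopped in case of negative interim analysis".

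The analysis sections do not carry this through. Protocol 7.3.1 says that "objective response rate (ORR) will be summarised and presented with 95% two-sided confidence intervals using the Clopper-Pearson method". SAP 7.4.1 uses the "objective response rate (ORR), defined as the proportion of patients with best overall response of CR or PR" and describes its Clopper-Pearson interval as exact: "ORR according to RECIST v1.1 will be summarised descriptively with 95% exact Clopper-Pearson confidence intervals (CIs". No readable part of either document gives a two-stage interval or an adjusted estimate. Protocol 7.1.2 leaves room only for unspecified robustness analyses in the SAP.

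**The concern.** Clopper-Pearson limits hold each tail at or below 2.5% when the sample size is fixed in advance. In these three groups it is not. A poor first stage freezes the group at 10 or 20 patients, and a better one takes it to 30 or 40. Low results can therefore arise in two ways, as a stopped group or as a continued group with few further responses. The fixed-sample formula treats each as if the other could not happen, so the two chances of missing the true rate add up.

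Confirmed ORR is a primary endpoint of Phase Ib, and protocol 3.2 says the results will inform decisions on later studies. A reader will naturally compare the upper limit with the planning rate (25%, 50%, 25%) to judge whether a group has fallen short. That is the limit affected.

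**Working it through.** **Inputs** (protocol 7.4 and Table 7.4: 1)

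| Group | n1 | Stop if responders | N | Planning ORR | Target at final |
|---|---|---|---|---|---|
| Cervical/anal | 10 | 0 | 30 | 25% | at least 6 |
| Skin | 10 | 0 to 2 | 30 | 50% | at least 12 |
| Vaginal/VSCC | 20 | 0 or 1 | 40 | 25% | at least 8 |

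**1. Reproduce the plan's figures.** The early-stop probability is P(Bin(n1, p) below the boundary).
- Cervical/anal: 0.75^10 = 5.6% (plan 6%).
- Skin: (1 + 10 + 45)/1024 = 5.5% (plan 5%).
- VSCC: 0.75^20 + 20 × 0.25 × 0.75^19 = 0.32% + 2.11% = 2.4% (plan 2%).

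The probability of reaching the target with the stop built in is 77.6%, 87.0% and 81.3% (plan 77%, 87%, 82%). All 38 probabilities in the table reproduce within 2 points. Ignoring the stop would give 79.7% and 90.0% for the two Cohort 6 groups, so the planning figures there account for it.

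**2. Upper-tail error at one point, by hand.** The Clopper-Pearson upper limit U for x/n solves P(Bin(n, U) ≤ x) = 0.025. Take VSCC at its planning ORR of 25%:
- Stopped: the limits for 0/20 and 1/20 are 16.8% and 24.9%, both below 25%. Contribution 2.43%.
- Continued: the limit for 4/40 is 23.7% (below 25%) and for 5/40 is 26.8% (above). P(continue and total ≤ 4) = 1.00%.
- Total 2.43% + 1.00% = 3.43%. With 40 patients fixed it would be P(Bin(40, 0.25) ≤ 4) = 1.6%.

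**3. The same sum over all true ORRs**

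| Group | Max within Table 7.4: 1 range | Max overall | At planning ORR | Minimum two-sided coverage |
|---|---|---|---|---|
| Cervical/anal | 1.7% | 4.4% (ORR about 31%) | 0.6% | 93.4% |
| Skin | 3.2% (about 46%) | 4.2% (about 56%) | 2.4% | 94.1% |
| VSCC | 3.5% (about 25%) | 3.5% | 3.4% | 94.2% |

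At the cervical/anal peak, just above 30.85%, the stopped branch gives 0.6915^10 = 2.50% and continuing with at most 4/30 adds 1.88%. The lower-limit error never exceeds 2.5% in any group. Coverage below 95% is confined to narrow bands, for example 26.8% to 27.0% in VSCC.

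**4. Stage-ordered limits.** Rank every stopped outcome below every continued one. For a continued group with s responders, U solves P(stop) + P(continue, total ≤ s) = 0.025, and L solves P(continue, total ≥ s) = 0.025. For VSCC 4/40 at U = 26.2%, this is 1.85% + 0.65% = 2.5%.

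| Result | Clopper-Pearson | Stage-ordered |
|---|---|---|
| VSCC 4/40 | 2.8% to 23.7% | 3.1% to 26.2% |
| VSCC 8/40 | 9.1% to 35.7% | 9.1% to 35.8% |
| Cervical/anal 6/30 | 7.7% to 38.6% | 7.8% to 39.4% |
| Skin 12/30 | 22.7% to 59.4% | 23.0% to 60.8% |

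With these limits each tail is at most 2.5%, and minimum coverage is 95.1% to 95.2%.

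**5. Bias of the raw ORR.** With n2 = N − n1, bias = (n2/N) × Σ over stopped x of P(x)(x/n1 − p).
- Cervical/anal at 25%: (2/3) × 0.0563 × (−0.25) = −0.9 points.
- Skin at 50%: (2/3) × (−0.5 − 4.0 − 13.5)/1024 = −1.2 points.
- VSCC at 25%: (1/2) × (0.0032 × (−0.25) + 0.0211 × (−0.20)) = −0.3 points.

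The largest values are −2.3 (cervical/anal, ORR about 9%), −3.8 (skin, about 27%) and −1.3 (VSCC, about 9.5%).

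**The case against.** **The analysis is descriptive.** Protocol 7.1.2 and 7.2 say so, and the stopping and target criteria are observed counts, not confidence limits. This stands, and it limits the consequence. It does not make an interval exact that is labelled so.

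**The largest errors lie outside the planned ranges.** This stands. The 4.4% is just above the top cervical/anal row (30%), and within that group's rows the upper tail stays below 2.5%. The 4.2% is above the top skin row (50%). VSCC is the exception: its maximum is next to its own planning rate.

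**A stopped group's upper limit is not at fault.** A reader might infer that a stopped group is being wrongly ruled out. The calculation does not support that. Under stage ordering the stopped outcomes keep their Clopper-Pearson limits at n1: 0/10 stays at 30.8%, 2/10 at 55.6%, 1/20 at 24.9%.

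**An unbiased estimate is not clearly better.** A reader might want the two-stage unbiased estimate (UMVUE) to replace the raw ORR. Among groups that continue, it moves further from the truth: for skin at a true 25%, the mean error rises from +4.0 to +11.9 points, and 3/30 would be reported as 30%. That is a trade-off, not a correction.

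**The stop may not be clean.** Protocol 3.1 lets recruitment run on during the interim and leaves the decision to the sponsor. Assuming 3 to 10 extra patients in a stopped group, the maximum upper-tail error is 2.8% to 3.6% and the maximum bias 0.4 to 2.5 points. The effect is mostly smaller but does not vanish; in VSCC with 5 extra patients it is still 3.5%.

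**Parts of the SAP are redacted,** including the entry after 7.4.1 in its contents. A supplementary two-stage analysis there cannot be excluded. The stated primary analysis would still be the fixed-sample one.

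**Conclusion.** The point holds as a modest, cheap correction. The planned interval is not exact in the three two-stage groups. Within the planning ranges its upper-tail error reaches 3.5% (VSCC) and about 3.2% (skin) instead of 2.5%. The practical effect falls on continued groups with few responders, as VSCC 4/40 shows: the planned interval excludes the 25% planning rate and the stage-ordered one does not. At the target counts the two intervals nearly agree. The raw ORR is low on average over the design, by about a point or less at the planning rates.

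This rests on the stop being followed at exactly 10 or 20 patients, and on the two Cohort 6 groups being reported separately. SAP 6.1 presents data by cohort, so the second is an assumption. For Cohort 7 alone the maxima are 3.5% and 1.3 points.

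It should not be read as inflated false-positive claims: the lower limit keeps its 2.5%.

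**What to change.** In SAP 7.4.1 and protocol 7.3.1, for squamous cervical/anal, squamous skin and vaginal/VSCC:

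- Report each group separately, including the two within Cohort 6.
- Keep the raw ORR as the lead estimate and add a stage-ordered exact 95% interval computed from the actual stage sizes, including any overrun.
- If Clopper-Pearson is also shown, do not call it exact, and state that it ignores the interim stop.
- Show a UMVUE, if at all, only as a supplement, noting that it is biased upward among groups that continue.

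Cohorts 4 and 5 have no futility look and stay as they are. The cost is a few sentences and a short program, with no extra patients or data. The downside is a somewhat wider interval for continued groups with low response and one more display to explain.
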